#### 8.1.4 During Surgery

During surgery, participants will be administered a short acting local anesthetic (lidocaine or mepivacaine with or without vasoconstrictor) and nitrous oxide; at the discretion of the oral surgeon. Topical anesthetics may also be used prior to the administration of the short acting local anesthetic. Long duration local anesthetics like bupivacaine are not permitted. No other perioperative analgesic or anesthetic agents are permitted. Perioperative corticosteroids are not permitted.

#### 8.1.5 Surgical Trauma Score

At the completion of the procedure, the surgeon will rate the degree of surgical trauma on a of (1) mild, (2) moderate or (3) severe. Only individuals with a surgical trauma rating of mild (1) or moderate (2) will be eligible to participate in the study.

#### 8.1.6 Postsurgery

During the post-surgery recovery period, participants will rest quietly, but will be encouraged not to fall asleep. Participants will be permitted to drink clear liquids following surgery. Participant may incorporate foods according to a soft diet following dosing beginning 60 minutes after dosing. Participants will not be allowed to eat 30 minutes prior to any planned assessments.

In order to qualify for randomization and continue in the trial, participants must have 'moderate' or 'severe' postoperative pain intensity on the Categorical Pain Rating Scale **and** a score of  $\geq 5$  on the NRS within 4.5 hours of the last suture.

Eligible participants will be assigned a participant randomization number and investigational products will be administered according to a generated randomization schedule (see Section 6.1.1).

Participants who have not met the randomization criteria within 4.5 hours from last suture or 14:30 h will not be randomized and may be discharged from the clinic, once deemed eligible by an Investigator. Prior to being released from the clinic, discharge procedures will be reviewed with the participant. When discharged, all participants will need to make prior arrangements for travel and should not drive themselves home.

After the baseline (pre-dose) pain intensity is determined, pain intensity and pain relief will be rated by participants at 0.5, 1, 1.5, 2, 3, 4, 5, 6, 7, 8, 9, 10, 11, and 12 hours (+/-5 minutes over the first 6 hours; +/-5 minutes from hours 7 through 12) post-dose, and immediately prior to the use of the first dose rescue medication.

CCI

CCI [REDACTED]

CCI [REDACTED]

CCI [REDACTED]

This answer will be recorded by the study coordinator in the case report form. CCI [REDACTED]

CCI [REDACTED]

CCI [REDACTED]

CCI [REDACTED]

Participants will stay awake during the entire 12 hour assessment. The order of the pain assessments is Pain Intensity, then Pain Relief, then query about any AEs. At hour 12 or immediately prior to the first dose of rescue medication (if prior to hour 12), study participants will be asked to provide a Global Assessment of investigational product after completion of the other assessments. Additionally, participants will have vital signs taken after surgery then at 1 and 12 hours post-dose.

Throughout the treatment period, the participants will be monitored for the occurrence of adverse events. Symptoms will be assessed by spontaneous reporting of AEs and by asking the participants to respond to a non-leading question such as “How do you feel?” or “Are you experiencing any other effects?” All reported or observed AEs will be collected and recorded on the case report form. The information will be based on signs and symptoms reported by the participant or observed by the study personnel staff during clinical evaluation.

If a participant has any clinically significant, trial-related abnormalities at the conclusion of the treatment period, the clinical monitor (or designated representative) should be notified and the participant should be asked to remain at the trial site until such abnormalities are stabilized or resolve. If the participant is unable or unwilling to remain at the trial site, the clinical monitor (or designated representative) should be notified, and the Investigator should make every effort

to arrange follow-up evaluations at appropriate intervals to document the course of the abnormalities.

Participants will be allowed the use of ice following the use of rescue medication. Ice will not be permitted for participants prior to randomization until after they have been administered rescue medication (if applicable). If participant has been administered rescue, ice will be given as requested by the participant for 20 minute increments. Upon completion of all trial procedures, participants will be discharged from the trial site. Participants will need to make prior arrangements for travel and should not drive themselves home.

## **8.2 Safety Assessments**

Safety measures will be analyzed for all participants in the safety population.

Adverse events will be collected throughout the treatment and safety follow-up periods and will be coded using the Medical Dictionary for Regulatory Activities (MedDRA) dictionary. Only treatment-emergent AEs will be included, i.e., AEs that begin or worsen after the first dose of the investigational products in the treatment period. The number and percent of participants who experience any event, by System Organ Class (SOC), and by Preferred Term will be displayed by treatment group. Tables will also be produced by severity and relationship to investigational product. Seriousness, severity, relationship to investigational product, duration, and outcome will also be listed.

Planned time points for all safety assessments are provided in the SoA.

### **8.2.1 Physical Examinations**

The physical examination (by means of inspection, palpation, auscultation) will be performed by qualified medical staff (e.g., a physician, oral surgeon, nurse practitioner or physician assistant) at the study site covering at least the organs of the head/neck, cardiovascular, and respiratory systems.

Abnormal physical examination findings are recorded either as medical history or as adverse events (see Section [10.3.1](#)).

### **8.2.2 Vital Signs**

Systolic and diastolic blood pressure and heart rate will be measured (in triplicates allowing one minute in between measurements) by a member of the investigator's team under the following conditions:

- Systolic blood pressure (after resting for at least 5 min in sitting position);
- Diastolic blood pressure (after resting for at least 5 min in sitting position);
- Heart rate (after resting for at least 5 min in sitting position);
- Measuring site: cuff to be placed on the right / left upper arm (if possible, the same arm will be used for all measurements in one participant); cuff location will be documented;
- Method: oscillometric by automatic measurement device.

Blood pressure is to be taken in triplicates, one minute apart to enhance accuracy as suggested in the FDA guidance (Assessment of Pressor Effect of Drugs, May, 2018).

### **8.2.3 Clinical Safety Laboratory Assessments**

Urine samples will be collected by a member of the investigator's team, for time points and parameters see Section 1.3.

### **8.2.4 Other Procedures and Variables**

Eligible participants will undergo an oral examination and a dental x-ray (radiograph) exam to confirm that impacted third molar teeth are present.

## **8.3 Adverse Events and Serious Adverse Events**

The definitions of an AE or SAE can be found in Section 10.3.

AE will be reported by the participant (or, when appropriate, by a caregiver, surrogate, or the participant's legally authorized representative or health care professional not involved in the study).

The investigator and any qualified designees are responsible for detecting, documenting, and recording events that meet the definition of an AE or SAE. They remain responsible for following up SAEs, or AEs considered related to the study intervention or study procedures, or those that caused the participant to discontinue the study.

### **8.3.1 Time Period and Frequency for Collecting AE and SAE Information**

All AEs and SAEs will be collected from the signing of the ICF until the follow up visit at the time points specified in the SoA (Section 1.3).

Medical occurrences that begin before the start of study intervention but after obtaining informed consent will be recorded on the Medical History/Current Medical Conditions section of the case report form (CRF) not the AE section.

All SAEs will be recorded and reported to the sponsor or designee immediately and under no circumstances should this exceed 24 hours, as indicated in Section 10.3.2. The investigator will submit any updated SAE data to the sponsor within 24 hours of it being available.

Investigators are not obligated to actively seek AE or SAE after conclusion of the study participation. However, if the investigator learns of any SAE, including a death, at any time after a participant has been discharged from the study, and he/she considers the event to be reasonably related to the study intervention or study participation, the investigator must promptly notify the sponsor.

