### 2.3 Benefit/Risk Assessment

Participants who need to have third molar extraction will be solicited to participate in this study. Participants who consent to participate may benefit by receiving a medical exam, dental radiographs and no-cost surgical procedures for teeth extraction. Furthermore, post-surgical participants will be provided continuous nursing care for approximately 12 hours after surgery. Potential risks of the surgical procedure include pain, dry socket, infection, swelling, bleeding, trismus, and lip or tongue numbness. Potential risks related to local anesthesia and mild sedation include paresthesia and drowsiness. Participants who experience a treatment failure can have the option of taking a standard rescue medication commonly used for post-operative pain relief. Potential study medication benefit will be relief of postsurgical pain, which is highly

prevalent following extraction of wisdom teeth. Potential risks of a single dose of OTC study medication are low and described in the Drug Facts Label.

During the study, participants will be closely monitored for evidence of adverse events. Weighing between the potential risks associated with the study, and given the ability to mitigate risks through close monitoring and routine peri-operative care, this study is considered clinically and ethically acceptable.

More detailed information about the known and expected benefits and risks and reasonably expected adverse events may be found in the naproxen sodium Investigator's Brochure and Aleve® Drug Facts Label.

CCI

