## **5.4 Screen Failures**

Screen failures are defined as participants who consent to participate in the clinical study but are not subsequently randomly assigned to study intervention. A minimal set of screen failure information is required to ensure transparent reporting of screen failure to respond to queries from regulatory authorities. Minimal information includes demography, screen failure details, eligibility criteria, and any serious adverse event (SAE).

Individuals who do not meet the criteria for participation in this study (screen failure) due to scheduling surgery may be rescreened. A previous dental x-ray if taken during the original screening visit can be used when rescreened. Rescreened participants should be assigned a new participant number.

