## **5.5 Run-in Failures**

A participant who, for any reason terminates the study after surgery and prior to the start of study drug administration (e.g., not meeting pain threshold) is regarded as a “Run-in failure”.

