#### Causal relationship to protocol-required procedure(s)

---

The assessment of a possible causal relationship between the AE and protocol-required procedure(s) is based on the question whether there was a “reasonable causal relationship” to protocol-required procedure(s).

Possible answers are “yes” or “no”

---

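### Protocol 8.3.1 collects adverse events from consent but files those that start before dosing as medical history, so non-serious surgical harms recognised before dosing normally get no AE record

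*Protocol*

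**What the plan says.** Three consecutive paragraphs of protocol 8.3.1 bear on events between consent and dosing.

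- First: "All AEs and SAEs will be collected from the signing of the ICF until the follow up visit". The Schedule of Activities (1.3) agrees, with AE assessment marked at screening, on Day 1 and at end of trial. SAP 6.9.2 also provides for AEs noted before the first dose.
- Second: "Medical occurrences that begin before the start of study intervention but after obtaining informed consent will be recorded on the Medical History/Current Medical Conditions" part of the CRF. The AE section is expressly ruled out, with no exception for serious events or for events caused by a study procedure.
- Third: "All SAEs will be recorded and reported to the sponsor or designee immediately and under no circumstances should this exceed 24 hours". This sentence has no exception for the pre-dose interval.

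The study procedures with most potential for harm fall in that interval. Protocol 2.3 says "Potential risks of the surgical procedure include pain, dry socket, infection, swelling, bleeding, trismus, and lip or tongue numbness", and it lists further risks for local anaesthesia and sedation. Protocol 8.3 makes investigators responsible for following AEs related to study procedures. Protocol 10.3.3 asks for an intensity grade and a yes/no judgement on causation by protocol-required procedures for AEs.

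Some participants have surgery but never reach dosing. Protocol 5.5 classes as a run-in failure anyone who "terminates the study after surgery and prior to the start of study drug administration", and 8.1.6 allows those who do not qualify to be discharged.

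**The concern.** A site cannot follow both of the first two paragraphs. If it follows the second, a bleed, an area of numbness or a reaction to the anaesthetic noticed before dosing becomes a medical-history entry. The intensity grade and the procedure-causality question belong to the AE record, so they would normally go unanswered. Yet these are harms that the trial's own procedures can cause, and protocol 2.3 names several of them as risks of taking part.

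Three things are at stake: a complete account of procedure-related harm, consistent recording across participants, and a clear CRF destination for a serious event that occurs before dosing. A related question is whether anyone is assigned to contact participants who had the surgery but were not dosed.

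**Working it through.** **1. Which events lose an AE record.** Surgery, then qualification on pain, then dosing all fall on Day 1. Dosing comes within 4.5 hours after surgery (protocol 6; 8.1.6 gives the same limit for qualifying, from the last suture). Taking the rules together:

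| Event | Governing text | AE record? |
|---|---|---|
| Non-serious, starts and is recognised before dosing, does not worsen | 8.3.1, second paragraph | Normally no |
| Starts before dosing, first detected after dosing | 10.3.1, events meeting the AE definition | Yes |
| Starts before dosing, worsens after it | Protocol 8.2; SAP 6.9.2 | Yes |
| Starts after dosing | Protocol 8.2, 8.3.1 | Yes, with procedure causality (10.3.3) |
| Serious, starts before dosing | 8.3.1, second and third paragraphs; 5.4 | Reportable within 24 hours; CRF page unclear |
| Non-serious, participant never dosed | 8.3.1, second paragraph | Normally no; the two post-dose routes cannot apply |

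The gap is the first and last rows, plus the unclear CRF page in the fifth.

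**2. Effect of moving these events to the AE page.** Protocol 8.2 counts an AE as treatment-emergent only if it starts or worsens after the product is taken. SAP 6.9.2 uses the calendar date of dosing. Surgery and dosing share that date, so under the SAP rule a surgical event recorded as an AE at, say, one hour before dosing would enter the treatment-emergent tables. Correcting 8.3.1 alone would therefore create a new error.

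**3. How many people are involved.** The plan's own figures come first.

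- Arm total (protocol 9.2): 5 × 30 + 2 × 15 = 180.
- Inflation for 5% drop-out: 180 / 0.95 = 189.5, rounded up to 190. The 190 reproduces.
- Protocol 4.1 and SAP 4.1 make 190 the number operated on and 180 the number randomised. Operated on but not randomised: 190 − 180 = 10, or 10 / 190 = 5.3%.
- Protocol 1.1 and 9.2 make 190 the number randomised. The number operated on but not dosed is then not given. It lies between 0 and 300 screened − 190 = 110, and the upper end includes people who never reach surgery.

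**4. Illustration of scale.** The documents give no rate of non-serious pre-dose harm. For assumed rates of 1%, 5% and 10%:

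- Expected events among 190 operated on: 190 × 0.01 = 1.9; 190 × 0.05 = 9.5; 190 × 0.10 = 19.
- Chance of at least one among 10 undosed participants, 1 − (1 − p)^10: 10%, 40% and 65%.

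**5. Follow-up of those not dosed.** The texts do not line up.

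- Protocol 4.1 (Follow-Up Phase) gives the 2-5 day contact to participants in general, timed from discharge, but describes its purpose by reference to treatment.
- Protocol 4.4 times the contact from surgery, inside the definition of study completion.
- Protocol 7.2 lists those below the pain threshold among the withdrawals and asks, if possible, for an early discontinuation visit as shown in the SoA. The SoA has no such column.
- Protocol 5.5 and 8.1.6 describe run-in failures as leaving the study or being discharged, and name no later contact.

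No text expressly assigns the contact to these participants, and none excludes them.

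**The case against.** The best defence is that protocol 10.3.1 ties an AE to use of study intervention, and the definition of study intervention in section 6 does not name surgery. Recording pre-dose occurrences as history fits that definition. Nor is the information lost, since SAP 6.5 codes medical history in MedDRA and lists it by subject. On this view the rule is a data-capture choice. This stands in part: the events remain visible in a listing. It does not resolve the conflict with the first paragraph of 8.3.1, the SoA, SAP 6.9.2 and the duty in 8.3 to follow procedure-related AEs. A history listing also carries neither the intensity grade nor the procedure-causality answer.

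A reader might also infer three stronger things that the documents do not support.

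- That surgical harms never get an AE record. Those that start, are first detected or worsen after dosing do, so dry socket or infection arising later is covered in dosed participants.
- That a pre-dose serious event could properly be filed without a 24-hour report. The reporting sentence covers all SAEs, protocol 5.4 keeps any SAE for people not randomised, and 8.3.1 requires notice of later-learned SAEs related to study participation. Only the CRF page is in doubt.
- That operated, undosed participants have no follow-up contact. Protocol 4.1, 4.4 and 7.2 speak of participants without limiting them to those dosed, and 10.1.4 says consent covers end-of-trial examinations after withdrawal. The contact is not expressly assigned, which is weaker than absent.

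**Conclusion.** The contradiction in 8.3.1 is real and should be corrected. Its effect is confined to non-serious surgical or anaesthetic harms that start and are recognised before dosing and do not worsen afterwards, including any such harm in a participant who is never dosed. These normally lack an AE record, an intensity grade and a procedure-causality judgement.

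Everyone operated on is exposed to the rule: about 190 under protocol 4.1, and at least about 190 under 1.1 and 9.2. The number of events cannot be derived from the documents, and the illustration above rests wholly on assumed rates. The figure of 10 operated but undosed holds only under protocol 4.1 and SAP 4.1.

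This concerns the safety record. Efficacy comparisons between treatments are unaffected.

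**What to change.** 1. **Protocol 8.3.1.** State that pre-dose events that are serious, or related to a protocol-required procedure, go on the AE/SAE page with the procedure-causality question answered. Send only other pre-dose occurrences to medical history. Write the SAE exception into the routing sentence.
2. **SAP 6.9.2.** Define treatment-emergent by time of dosing instead of date, in line with protocol 8.2. List Day 1 pre-dose surgical events separately as non-treatment-emergent. That listing must reach beyond the Safety population, which protocol 9.3 limits to those who took the product.
3. **Follow-up.** Reconcile protocol 4.1, 4.4, 5.5, 7.2 and 8.1.6 on whether the existing 2-5 day contact covers participants operated on but not dosed.
4. **Counts.** Reconcile protocol 4.1 and SAP 4.1 with protocol 1.1 and 9.2 on whether 190 is the number operated on or the number randomised.

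The cost is protocol wording, a short SAP edit, use of an existing CRF page and a few more AE entries that are not treatment-emergent. If the contact is confirmed for undosed participants, add about 10 calls on the protocol 4.1 count; on the other count the number is not stated.

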### **8.3.2 Expected Adverse Events**

For this study, the applicable reference document is the most current version of the DFL and IB for naproxen and caffeine. If relevant new safety information is identified, the information

will be integrated into an update of the safety information and distributed to all participating sites.

The expectedness of AEs will be determined by the sponsor according to the applicable reference document and according to all local regulations.

### 8.3.3 Method of Detecting AEs and SAEs

The method of recording, evaluating, and assessing causality of AE and SAE and the procedures for completing and transmitting SAE reports are provided in Section 10.3.

Care will be taken not to introduce bias when detecting AEs and/or SAEs. Open-ended and non-leading verbal questioning of the participant is the preferred method to inquire about AE occurrences.

### 8.3.4 Follow-up of AEs and SAEs

After the initial AE/SAE report, the investigator is required to proactively follow each participant at subsequent visits/contacts. All SAEs will be followed until resolution, stabilization, the event is otherwise explained, or the participant is lost to follow-up (as defined in Section 7.3). Further information on follow-up procedures is given in Section 10.3.

### 8.3.5 Regulatory Reporting Requirements for SAEs

Prompt notification by the investigator to the sponsor of an SAE is essential so that legal obligations and ethical responsibilities towards the safety of participants and the safety of a study intervention under clinical investigation are met.

The sponsor has a legal responsibility to notify both the local regulatory authority and other regulatory agencies about the safety of a study intervention under clinical investigation. The sponsor will comply with country-specific regulatory requirements relating to safety reporting to the regulatory authority, Institutional Review Boards (IRB)/Independent Ethics Committees (IEC), and investigators.

Investigator safety reports must be prepared for suspected unexpected serious adverse reactions (SUSAR) according to local regulatory requirements and sponsor policy and forwarded to investigators as necessary.

An investigator who receives an investigator safety report describing an SAE or other specific safety information (e.g., summary or listing of SAEs) from the sponsor will review and then file it along with the Investigator's Brochure and will notify the IRB/IEC, if appropriate according to local requirements. Send the SAE CRF pages and complementary forms to:

PPD [redacted] or Fax: PPD [redacted] (in the USA)

